	
MODIFY studies with bezlotoxumab vs. placebo (Zinplava Package insert).
 
Those patients meeting the study inclusion/exclusion criteria will be offered open-label Bezlotoxumab infusion. This active intervention arm will have baseline stool samples collected for C difficile culture and typing at study entry and upon CDI relapse, if any
 
The comparator groups will be
 
 1. The historical control group from the Wong study, and 2. A concurrent observational arm – consisting of those patients otherwise eligible for the study, but : 
 A. Not consenting to study enrolment, and B. Taking no form of CDI prophylaxis (no oral vancomycin, metronidazole or fidaxomicin use as defined below). 
All cohort members will be subject to standardized chart review for baseline parameters at study entry, and structured followup by chart review every 2 weeks for 8 weeks for CDI relapse (the primary endpoint), tolerability of study drug (if administered) , length of hospitalization/ICU stay or death.
 
Use of CDI prophylaxis will be adjudicated to see if it conforms to the standards established in the Wong study – prophylaxis used for at least 50% of the duration of the concomitant antibiotics course and at least up to 72 hrs before the end of the concomitant antibiotics. Patients receiving any such prophylaxis will be excluded from the per-protocol analysis, which will be the primary analysis. Secondary analysis will also be performed on an intent-to-treat basis, where group assignment is determined based on use of prophylaxis at study entry only.
 
This design was chosen to parallel that of the retrospective Wong study at our same site – to allow comparisons with the historical treatment groups in that study.

2.4 Study Flowchart
	<pre> graph TD Cdiff_dx[14-90 days Cdiff dx] --> Inpatient Inpatient --> On_Abx{On Abx?} On_Abx -- No --> Follow_daily[Follow daily] On_Abx -- Yes --> On_CDI_ppx{On CDI ppx?} On_CDI_ppx -- Yes --> Offer_Bezlo[Offer Bezlo Study] Offer_Bezlo --> Enrol[Enrol] Offer_Bezlo --> Cdiff_Cx[C diff Cx and f/u 8 wks] On_CDI_ppx -- No --> Decline[Decline] Decline --> Follow_8_wk[Follow for 8 wk] Follow_8_wk --> Relapse_no_ppx[Relapse, no ppx No Relapse, no ppx] Follow_8_wk --> Relapse_Bezlo[Relapse, Bezlo No Relapse, Bezlo] </pre>

2.5 Study
	
STUDY DESIGN

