--	---

	 L A A B B C C D D E E F F G G H H H L	
2.6 Study Duration	
Estimate of 1 year required to recruit 50 patients (from an estimated 150 eligible) and another 6 months to complete the study analysis. A computer simulation indicates there should be 150 eligible subjects in 1 year. Of these, ~50 will be on prophylaxis and ~50 will decline participation and will be followed as no prophylaxis controls.
	
2.7 Statistical Analysis and Sample Size Justification	
The PI and local statistician will be responsible for analyzing the study data.
 
Variables/Time Points of Interest
 
The primary outcome variable is relapse of CDI within 8 weeks of study entry. Secondary outcomes are relapse of CDI within 4 weeks of study entry (the interval with highest protective antibody levels), all-cause mortality, time to relapse and duration of hospitalization.
 
Baseline variables collected for each subject include : age, gender, number/dates/treatment of prior CDI episodes, current PPI use and H2-blocker use, Charlson score, immunosuppression, Inflammatory Bowel Disease or Irritable Bowel Syndrome, use of cathartics/lactulose, and indication for current antibiotics.
 
Variables related to the past CDI episode include markers of disease severity : WBC, fever >100.5°F, creatinine, albumin – to generate a Zar score (Zar,2007)
 
Statistical Methods
 
The analysis population is the per-protocol population, with 2 major comparator groups – those receiving Bezlotoxumab and those with no prophylaxis. The latter will be comprised of 3 subgroups – the control group from the Wong study and 2 concurrent observation groups- a PASSIVE followup group of subjects undergoing chart review , and an ACTIVE followup group of subjects declining study drug but agreeing to phone followup at 8 weeks. All groups will be compared across baseline parameters cited above. Risk factors pre-specified for recurrent CDI include age, immunocompromise, and severe CDI will be compared across groups, and tested for associations for the major outcomes of CDI relapse and mortality at 4 weeks and 8 weeks.
 
In the Wong study, there was a remarkably equal distribution of variables among the
	

[figure not shown]

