antibiotic prophylaxis and no prophylaxis groups. We similarly expect no imbalance between our current study and observation groups in terms of risk factor distribution, though self-selection bias will be considered at the interim analysis after 30 intervention patients are enrolled.

Categorical variables will be compared using chi-square and Fisher's Exact analysis and continuous variables will be compared using Mann-Whitney analysis, with $p < 0.05$ considered to be significant.

In survival analysis (Kaplan-Meier), time to CDI relapse is defined from the date of bezlotoxumab study dosing or study refusal - to the date of relapse and limited by a maximum observable window of 8 weeks from the dose of bezlotoxumab. Subjects are censored on the date of death, if death occurred within the observable window, or at the beginning of a new potential antibiotic prophylaxis course (i.e.. If within the 8 week observation period there is receipt of metronidazole, oral vancomycin or fidaxomicin.) or receipt of fecal microbiota transplant. A Cox proportional hazards model will be used for group comparison when adjusting for covariates.

The survival analysis from the Wong study, demonstrating the benefits of antibiotic prophylaxis on preventing relapsed CDI, is summarized in the following figure:

Relapse Free Duration

For the second objective, rates of CDI relapse will be compared among study subjects with or without *C. difficile* colonization at study entry. This is an exploratory study to inform future studies. It is expected that 20% of subjects will be colonized at study entry (based on Sunkesula, 2013) –the expected number of these that relapse is unknown, as data is conflicting on whether colonization is protective or predictive of relapse.

Power/Sample Size:

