Estimates of group size and expected antibiotic prophylaxis outcomes are derived from the Wong and Van Hise studies which have similar or nearly identical design to the current proposal, albeit retrospective. In the Wong study, of 248 enrolled subjects, 104 received prophylaxis with metronidazole (n=63 total, 19 combined with vancomycin) or vancomycin (n=60), and 144 did not. In this latter group, 86 were \geq 60 yrs old of whom 23 relapsed, for a relapse rate of 26.7%. For the bezlotoxumab arm, the expected benefit is between a 43-54% reduction in relapse incidence (Gerdinger, 2018), with the variability based on the number of risk factors for CDI relapse in our population – all have at least 1 risk factor : most with age >65 and all with concurrent high-risk antibiotics. The expected CDI relapse rate in the active arm is therefore 12.2-15.2%. Thus

1. We need 62 bezlotoxumab subjects (at 12.2% relapse) to be 80% powered to detect a difference in outcomes vs. the no prophylaxis control population (with a relapse rate of 26.7%), with a two-tailed alpha=0.05.
2. We need 103 bezlotoxumab subjects (at 15.2% relapse) to be 80% powered to detect a difference in outcomes vs. the no prophylaxis control population (with a relapse rate of 26.7%), with a two-tailed alpha=0.05.

In 1 year, we expect 50 bezlotoxumab subjects and 50 no-prophylaxis controls in the prospective cohort. The numbers of subjects in the no-prophylaxis observational arms can be supplemented by retrospective chart reviews incorporating the same analysis used in the prospective study, or by merging with the control arm of the Wong study.

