Given the prospective design, with more data available regarding relapse than in the Wong study (wherein outpatient records were not yet electronic) and the fact that relapse rates in the control group in the MODIFY studies were 39% in those over 65, its possible that more relapses will occur in the no-prophylaxis group than the 26.7% expected. This would lower the numbers needed to show a significant benefit. An interim analysis is planned after 6 months or 30 subjects enrolled, to re-assess realistic timelines for achieving significant results from this project. Notably, this is a pilot study which if it meets targets, could potentially be extended by 3 to 6 months to achieve statistically significant power. Alternatively, if study effects exceed expectations, a placebo-controlled design could be considered moving forward- for the pilot study, this is precluded by the larger sample size anticipated for such a project.

2.8 Specific Drug Supply Requirements	
The Bezlotoxumab drug supplies will be open label and provided by MSD.
 
The institution's research pharmacy will require bulk supplies from MSD (one large container of 10 courses at 1 time). As bulk supplies are provided by MSD, our institution's pharmacy will be responsible for preparing individual patient doses. A description as to how the clinical supplies are to be packaged and labeled for each patient will be added to the protocol.
 
Note: At conclusion of the study or upon drug expiration, the MSD GRS will be responsible for issuing a Drug Disposition Letter to the investigator for US based studies.
 
The investigator will be responsible for the destruction of the supplies at the study center pursuant to the ICH/GCP Guidelines, local regulations and the investigator's institutional policies. Clinical supplies will be received by a designated person (research pharmacist) at the study site, handled and stored safely and properly, and kept in a secured location to which only the investigator and designated assistants have access. Clinical supplies are dispensed in accordance with the protocol. The investigator is responsible for keeping accurate records of the clinical supplies, the amount dispensed to and returned by the patients, and the disposition at the end of the study.

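### Historical and concurrent controls are combined with no study-era term, so about 63% of any relapse shift shared by the prospective groups enters the bezlotoxumab contrast

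*Combined protocol and SAP*

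**What the plan says.** Section 2.7, Statistical Methods, names two major groups, bezlotoxumab and no prophylaxis. Of the second it says "The latter will be comprised of 3 subgroups": the control group of the centre's earlier retrospective study, and two concurrent groups (PASSIVE, by chart review; ACTIVE, with a phone call at 8 weeks). Two other places differ. Section 2.3 numbers the historical and the concurrent controls as separate comparators. The Power/Sample Size text treats merging with the historical arm as one optional way to add controls.

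For the tests, "Categorical variables will be compared using chi-square and Fisher's Exact analysis", and for time to relapse "A Cox proportional hazards model will be used for group comparison when adjusting for covariates". The Cox covariates are not listed. Neither study era nor data source is named as an adjustment variable, and no comparison of relapse between historical and concurrent controls is planned.

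The Power/Sample Size text also says that relapse data are fuller now than in the retrospective study, whose outpatient records were not yet electronic. It adds that "its possible that more relapses will occur in the no-prophylaxis group than the 26.7% expected", cites 39% in control patients over 65 in the pivotal trials, and concludes that a higher control rate would reduce the numbers needed.

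**The concern.** No historical patient received bezlotoxumab, so in a pooled comparison treatment is partly confounded with era. A change in practice, case mix or detection that affects treated patients and concurrent decliners alike is absent from the historical controls, and part of it is read as a drug effect. The listed baseline variables are mostly patient characteristics, and adjusting for them does not correct a change in how completely relapse is captured.

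The plan itself describes such a change in capture. If it raises observed relapse, pooling masks a real benefit and can suggest harm. The concurrent decliners carry the information that separates era from drug, but a merged control group hides it. Because the sections disagree on merging, the choice could also be made after the data are seen.

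**Working it through.** **Inputs.** From Power/Sample Size: historical controls ("In this latter group, 86 were" aged 60 or over) with 23 relapses, 23/86 = 26.7%; 50 bezlotoxumab and 50 concurrent controls expected; planned relapse on drug 12.2-15.2% (a 43-54% reduction); two-sided alpha 0.05. The size of any era shift is not given, so it is varied as an assumption.

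**Step 1: the plan's own figures.** The stated 62 and 103 subjects reproduce from the one-sample formula

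n = [(1.960·√(p0(1−p0)) + 0.842·√(p1(1−p1))) / (p0−p1)]², with p0 = 0.267.

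- p1 = 0.122: [(0.867 + 0.275)/0.145]² = 62.1
- p1 = 0.152: [(0.867 + 0.302)/0.115]² = 103.4

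So 26.7% is treated as a known constant, with no allowance for its sampling error or for drift. A two-sample 1:1 calculation at 12.2% gives 116 per group.

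**Step 2: how much of a shift carries over.** Let r be the rate shared by both prospective groups, with no drug effect. The expected pooled control rate is (23 + 50r)/136, and the spurious difference (control minus treated) is (86/136)(0.267 − r) = 0.632(0.267 − r).

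- r = 39%: pooled control (23 + 19.5)/136 = 31.3%; treated looks 7.8 points worse, risk ratio 1.25.
- r = 16%: pooled control (23 + 8)/136 = 22.8%; treated looks 6.8 points better, risk ratio 0.70.

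**Step 3: rejection rate with no drug effect.** Exact enumeration of the uncorrected chi-square, 50 treated v 50 concurrent + 86 historical. The first figure holds the historical count at 23; the second lets it vary binomially.

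| Shared rate | Pooled, total | Of which favouring drug | Concurrent only, 50 v 50 |
|---|---|---|---|
| 16% | 12.5% / 15.4% | 12.5% / 15.3% | 5.5% |
| 20% | 6.2% / 8.4% | 6.0% / 7.9% | 5.2% |
| 26.7% (no shift) | 3.2% / 5.1% | 1.5% / 2.3% | 5.1% |
| 35% | 8.9% / 11.3% | 0.2% / 0.4% | 4.9% |
| 39% | 15.5% / 17.8% | 0.1% / 0.2% | 5.2% |

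Total error passes 10% only when the shared rate falls to about 17-19% or rises to about 34-36%.

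**Step 4: power (chi-square, 50 treated).**

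| Control rate in prospective groups | True reduction | Pooled | Concurrent only |
|---|---|---|---|
| 26.7% | 54% | about 57% | 46% |
| 39% | 54% | about 44% | 66% |
| 39% | 43% | about 20% | 45% |

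At the plan's rounded 12.2% v 26.7%, the first row is 58-59% pooled and 46% concurrent only. A higher control rate raises power against concurrent controls, as the plan says, but lowers it for the pooled comparison.

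**Step 5: the Cox model.** In 2,000 simulated trials per setting with no drug effect (exponential times, 56-day window), the model without an era term rejected in 15.0% at a shared 39% (median hazard ratio 1.31) and in 11.5% at 16% (0.66). With an era term the figures were 4.5% and 3.8%, with a median hazard ratio of 1.00 in both.

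**The case against.** **Inflation is not built into the design.** A reader might infer that pooling more than doubles the false-positive rate as a matter of course. The documents do not support that. With no shift the total is 3-5%, and passing 10% needs a shift of roughly 8 points or more, a size the documents never state. Nor does the whole of a shift count as drug effect; the share is 63%. This stands in full.

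**False benefit is not the documented risk.** A reader might also infer that pooling will manufacture a benefit. Nothing in the documents suggests that untreated relapse has fallen; the 16% row is an assumption. In the only direction the plan raises, false findings of benefit are at most 0.4% in the rows above. The plan calls the rise possible, not expected, and 39% is an outside figure for patients over 65, not a projection for this cohort. This also stands, but the cost in that direction is lost power and spurious harm.

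**Pooling is not settled, and an era term is not excluded.** Section 2.3 separates the comparators, merging is optional elsewhere, and the Cox covariates are open. The baseline list includes dates of prior CDI episodes, from which calendar period could be derived. True, but nothing commits the analysis to using it, and the disagreement between sections is itself a defect.

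**Which historical controls enter matters.** The full control group is 144 patients. At an assumed 20.8% relapse (the institutional rate in section 2.2), rejection at a shared 16% is 5.6% with the historical count fixed, rather than 12.5%.

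**Concurrent-only is no cure.** Consenters and decliners may differ. Section 2.7 undertakes to consider self-selection at the interim analysis, and the 5% figures assume it away. With an era term the historical patients add almost nothing to the drug contrast, although section 2.3 says the design was chosen to allow that comparison. These are real costs.

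**Conclusion.** The point holds conditionally. Followed as written, section 2.7 biases the bezlotoxumab contrast by about 63% of any shift shared by the prospective groups, and provides nothing to detect or remove it. The documented concern is upward: at a shared 39%, about 15-18% false rejections, nearly all toward harm, and power of about 44% rather than 66% for a true 54% reduction. That runs against the plan's expectation that a higher control rate makes the study easier. A downward shift to 16% would give about 12-15% false benefit, but only as an unsupported assumption.

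These sizes rest on 50 treated, 50 concurrent and 86 historical controls, an uncorrected chi-square test, and one relapse rate common to treated patients and decliners under no drug effect. This should be changed before analysis; it does not show that the study would reach a false conclusion.

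**What to change.** 1. Reconcile section 2.3, Statistical Methods and Power/Sample Size so that they state one rule on whether and how the control sources are combined.
2. In section 2.7, make bezlotoxumab v concurrent no-prophylaxis controls (PASSIVE plus ACTIVE) the lead contrast for 8-week relapse, adjusted for the baseline risk factors already collected, because consenters and decliners may differ.
3. In any Cox model that includes historical controls, or retrospective chart-review controls from earlier years, add an era indicator or stratify by era.
4. Report the pooled comparison as supportive, next to the concurrent-versus-historical control difference in relapse with its 95% confidence interval.

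This changes wording only and needs no new patients or data. The cost is precision: if there is no shift, power at 12.2% v 26.7% with 50 treated is about 46% instead of about 58-59%. The lead contrast also stays open to self-selection that the measured covariates do not capture, and the report should say so.

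### Mortality at 4 and 8 weeks is a declared outcome of a non-randomised comparison, but no covariate-adjusted analysis is tied to it (minor)

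*Combined protocol and SAP*

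**What the plan says.** Everything below is in section 2.7 unless another section is named.

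- **Outcome.** The secondary outcomes include "all-cause mortality, time to relapse and duration of hospitalization". Under Statistical Methods, "Risk factors pre-specified for recurrent CDI include age, immunocompromise, and severe CDI will be compared across groups, and tested for associations for the major outcomes"; the sentence ends by naming relapse and mortality at 4 and 8 weeks as those outcomes.
- **Groups.** Section 2.3 offers open-label drug to eligible patients and follows those who do not consent as concurrent controls. For the no-prophylaxis comparator, "The latter will be comprised of 3 subgroups": the historical control group and two concurrent observation groups.
- **Methods.** "Categorical variables will be compared using chi-square and Fisher's Exact analysis". The Kaplan-Meier paragraph defines one endpoint, time to CDI relapse, and censors at death. It closes by providing a Cox model for covariate adjustment, without listing the covariates.
- **Baseline data.** The variables collected for each subject include "current PPI use and H2-blocker use, Charlson score, immunosuppression", and "All groups will be compared across baseline parameters cited above".
- **Imbalance.** "We similarly expect no imbalance between our current study and observation groups in terms of risk factor distribution", although "self-selection bias will be considered at the interim analysis after 30 intervention patients are enrolled".

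**The concern.** Consent decides who is treated. If sicker patients or their surrogates decline more often, crude mortality on bezlotoxumab will look too low; if they accept more often, too high. The documents do not show which is likelier.

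The planned steps can reveal such a difference but do not correct for it. A baseline comparison shows imbalance. Testing a risk factor against death shows that the factor is prognostic. Considering self-selection at the interim has no stated analytic consequence. None of these changes the estimated mortality difference between the groups. The expectation of balance is drawn from a historical comparison of patients with and without antibiotic prophylaxis, and those groups were not formed by accepting or refusing a study infusion.

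At stake is a reported outcome that may partly reflect who consented.

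**Working it through.** **Inputs from the documents.** Section 2.7 expects 50 bezlotoxumab patients and 50 concurrent controls. The historical controls aged 60 or over number 86, with 23 relapses; no deaths are reported for them. The plan gives no mortality rate, Charlson distribution or power for mortality, so there is no figure of its own to reproduce.

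**Assumptions (illustrative).** No drug effect. Patients are of low or high risk by true prognosis, with 8-week mortality pL v pH of 5% v 20%, or more narrowly 8% v 16%. The high-risk share is h1 = 30% or 40% among treated patients and h0 = 50% among controls. Reversing the imbalance reverses the sign of the bias. A Charlson cut classifies prognosis with sensitivity = specificity = s.

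**Step 1: crude bias = (h1 − h0) × (pH − pL), in absolute size.**
- 0.20 × 0.15 = 3.0 points; 0.10 × 0.15 = 1.5 points
- 0.20 × 0.08 = 1.6 points; 0.10 × 0.08 = 0.8 points

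**Step 2: set against chance.** For 5%/20% and 30 v 50%, expected mortality is 0.05 + 0.30 × 0.15 = 9.5% treated and 0.05 + 0.50 × 0.15 = 12.5% control. The SD is √(0.095 × 0.905/50 + 0.125 × 0.875/50) = 6.25 points, and the root mean square error (RMSE) is √(6.25² + 3.0²) = 6.9. The bias is about half an SD. Expected deaths are 50 × 0.095 = 4.75 and 50 × 0.125 = 6.25, about 11 in all.

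**Step 3: bias left after Mantel-Haenszel adjustment by the cut.** Worked case, same scenario, s = 0.8:
- Cut-positive share: treated 0.30 × 0.8 + 0.70 × 0.2 = 0.38; control 0.50.
- Mortality if cut-positive: treated (0.24 × 0.20 + 0.14 × 0.05)/0.38 = 14.47%; control (0.40 × 0.20 + 0.10 × 0.05)/0.50 = 17.0%. Difference −2.53 points, weight 19 × 25/44 = 10.80.
- Mortality if cut-negative: treated (0.06 × 0.20 + 0.56 × 0.05)/0.62 = 6.45%; control (0.10 × 0.20 + 0.40 × 0.05)/0.50 = 8.0%. Difference −1.55 points, weight 31 × 25/56 = 13.84.
- Weighted mean: (10.80 × −2.53 + 13.84 × −1.55)/24.64 = −1.98 points.

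The same formula for the other cases (points of bias, absolute):

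| Mortality, high-risk shares | Crude | s = 1.0 | 0.9 | 0.8 | 0.7 |
|---|---|---|---|---|---|
| 5%/20%, 30 v 50% | 3.0 | 0 | 1.14 | 1.98 | 2.55 |
| 5%/20%, 40 v 50% | 1.5 | 0 | 0.55 | 0.97 | 1.26 |
| 8%/16%, 30 v 50% | 1.6 | 0 | 0.61 | 1.05 | 1.36 |
| 8%/16%, 40 v 50% | 0.8 | 0 | 0.29 | 0.52 | 0.67 |

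The zero at s = 1.0 is true by construction.

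**Step 4: total error, by simulation (200,000 trials per case).**
- 5%/20%, 30 v 50%: crude RMSE 6.9; adjusted 6.2, 6.3, 6.6 and 6.8 as s falls from 1.0 to 0.7.
- 5%/20%, 40 v 50%: crude 6.6; adjusted 6.3 to 6.6.
- 8%/16%, either imbalance: crude about 6.5; adjusted 6.4 to 6.5.
- Precision hardly changes. For s = 1.0 the SD is 6.3 crude v 6.4 adjusted at 8%/16%, 30 v 50%, and 6.6 v 6.5 at 5%/20% with no imbalance.
- The mean adjusted 95% half-width is 11.7 to 12.6 points.

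**The case against.** **The Cox sentence could cover death.** It is not expressly limited to relapse. Deaths are sought by chart review every two weeks (section 2.3) and their dates are needed for censoring, so the model could be fitted to mortality. This stands in part. A reader might infer that the plan rules out any adjusted mortality analysis, and the text does not support that. But the sentence closes a paragraph that defines only time to relapse and censors at death. Read generously, it still does not say that mortality will be adjusted, or for what.

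**Charlson score may not be left out.** The risk-factor list is introduced with the word include, so it need not be exhaustive, and Charlson score is compared across groups. That stands: one cannot say that Charlson will not be examined against mortality, only that it is not named.

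**The gain is small.** This also stands. In the most favourable scenario RMSE falls from 6.9 only to 6.6 to 6.8 when Charlson captures prognosis at 70 to 80%; at 8%/16% there is almost no gain. Patients with congestive heart failure or not expected to survive 8 weeks are excluded, which narrows the prognostic spread. No stated decision rule uses the mortality comparison, and SAEs go to a separate Safety Officer (section 2.9).

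**The pooled analysis may not be possible.** The documents report neither deaths nor Charlson scores for the historical group. A pooled 50 v 136 (50 + 86) mortality comparison would assume that both exist, so the adjusted estimate should rest on the concurrent controls.

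**Conclusion.** The point holds as a minor one. Mortality is a declared outcome of a self-selected comparison, and no adjusted analysis is clearly tied to it, although a comorbidity index is already collected. Under the assumed inputs the crude bias is 0.8 to 3.0 points, at most about half an SD for 50 v 50. Adjustment removes between about 15% of it (3.0 to 2.55 points at s = 0.7) and about 60% (3.0 to 1.14 at s = 0.9); only a perfect cut removes it all.

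A reader might go further and infer that the mortality result will favour the drug, or that harm will be hidden. The documents support neither. They give no consent pattern, so the direction is unknown. The only mortality signal they cite is in congestive heart failure, which is excluded, and the study is described as a pilot. Nor would the adjusted estimate settle safety: an interval of about ±12 to 13 points cannot establish or exclude harm.

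The sizes depend wholly on the assumed rates, imbalance and accuracy of the Charlson cut. The reading of the methods text does not.

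**What to change.** Add two or three sentences to section 2.7:

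- Beside the crude result, report the bezlotoxumab v no-prophylaxis mortality comparison at 4 and 8 weeks with a 95% interval, using age and Charlson score as covariates fixed before outcomes are seen. Choose one form in advance: a small regression, a Mantel-Haenszel risk difference by a pre-fixed Charlson cut, or the existing Cox model extended to time to death, with death as the event. About 11 expected deaths leave no room for a longer covariate list.
- Base the adjusted estimate on the concurrent controls. Add the historical group only if both 8-week deaths and Charlson score are available for it, and state which applies.
- Name Charlson score among the factors tested for association with mortality.
- Label the result descriptive and state that residual confounding is likely.

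The cost is one extra analysis of data already collected, a wide interval and possibly a very small loss of precision. Confounding by the acuity of the current infection would remain; if that drives consent, Charlson score may correct little. The crude result stays in place.
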